4.3 Safety Objectives

The safety objectives of the study are to monitor and assure safety of subjects during and after the experimental sessions by assessing physiological effects, psychological distress, adverse events, spontaneously reported reactions and suicidality.

- Suicidality will be assessed with the Columbia Suicide Severity Rating Scale (C-SSRS) during visits prior to experimental sessions, twice during experimental sessions, and several times after each experimental session, with comparisons made between subjects in each condition.
- Subjective Units of Distress (SUD) scores and vital signs including blood pressure, heart rate and temperature will be measured during each experimental session, and results will be compared between groups.
- Serious adverse events, adverse events and spontaneously reported adverse events ("reactions") will be collected during the study according to Section 8.5.

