8.2 Safety Measures

Columbia Suicide Severity Rating Scale (C-SSRS)

Subjective Units of Distress (SUD)

General Well-being (GWB)

Vital signs (systolic blood pressure (SBP), diastolic blood pressure (DBP), heart rate (HR), body temperature (BT))

Adverse Events (AE), including Spontaneously Reported Reactions (SRR)

8.3 **Process Measures**

Belief of Condition Assignment

Reactions to Research Participation Questionnaire (RRPQ)

Long-term Follow-up Questionnaire (LTFU Questionnaire)

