9.9.4 Safety Analyses

The primary measure of safety will be the reporting of adverse events. The Adverse events considered are Treatment Emergent Adverse Events (TEAE) defined as those AE's that occurred after dosing and existing medical history diagnoses that worsened during the study. Verbatim terms on case report forms will be mapped to preferred terms and system organ classes using the MedDRA dictionary. For incidence reporting if a subject has more than one AE mapped to the same preferred term, that AE will be reported only once using the highest severity and closest relationship to study drug. Subject incidence of AEs will be displayed by treatment group by stage and by system organ class. AEs will also be summarized by severity and relationship to study drug. Subject incidence of SAEs by treatment group by stage will also be displayed. In addition to the listing of all AEs, a listing of SAEs and a listing of AEs leading to discontinuation of study drug will be included.

Summary tables of frequency listings of commonly reported AEs (Spontaneously Reported Reactions) mapped to preferred terms will be displayed during and after each experimental session by Stage 1 treatment group.

Columbia Suicide Severity Rating Scale (C-SSRS)

Suicidal ideation and behavior will be summarized according to suggestions made in the Columbia-Suicide Severity Rating Scale Scoring and Data Analysis Guide [2]. A positive response for suicidal ideation is counted when a subject answers "yes" to any one of the five suicidal ideation questions (Categories 1-5) on the C-SSRS, i.e. a score > 0 for suicidal ideation score. Serious suicidal ideation is a suicidal ideation score of 4 or 5. A positive response for suicidal behavior occurs when a subject answers "yes" to any one of the five suicidal behavior questions (Categories 6-10) on the C-SSRS, i.e. a score > 0 for suicidal behavior score. The number and percent of positive responses of Positive Ideation, Serious Ideation, and Positive Behavior will be tabulated by Stage I treatment group and time period. Compare lifetime serious suicidal ideation and positive behavior frequencies to cumulative frequencies anytime during the study until end of Stage 1 and Stage2.

Subjective Units of Distress (SUD)

Descriptive statistics for SUD scores will be calculated by Stage 1 treatment group and time period with counts and percentages.

Vital signs

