Vital signs (heart rate, body temperature, systolic and diastolic blood pressure) will be summarized using descriptive statistics at baseline and at each post-baseline time point. Occurrences of systolic and diastolic blood pressure, heart rate, and body temperature readings above the pre-determined cutoff will be displayed with numbers and percentages by timepoint.

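### Do the SAP's safety tables mix 25 mg and 125 mg sessions, because vital signs have no named dose grouping and Stage 2 and lead-in data have no stated place?

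*SAP*

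**What the plan says.** SAP 9.9.4 treats the safety measures one after another.

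- **Vital signs** "will be summarized using descriptive statistics at baseline and at each post-baseline time point". For blood pressure, heart rate and temperature, "readings above the pre-determined cutoff will be displayed with numbers and percentages by timepoint". Neither sentence names a dose or treatment group.
- **Spontaneously reported reactions** "will be displayed during and after each experimental session by Stage 1 treatment group".
- **C-SSRS** results are "tabulated by Stage I treatment group and time period". A further sentence compares lifetime history with cumulative on-study counts and names the ends of both stages.
- **SUD:** "Descriptive statistics for SUD scores will be calculated by Stage 1 treatment group and time period with counts and percentages".
- **Adverse events:** "Subject incidence of AEs will be displayed by treatment group by stage and by system organ class". SAP 8.2 counts reactions among the adverse events.

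SAP 4.3, on SUD and vital signs, says that they "will be measured during each experimental session, and results will be compared between groups". Protocol 12.0 plans descriptive statistics for every measurement, overall and by dose condition. It also plans a formal or informal comparison of peak vital signs after active-placebo and full-dose sessions.

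SAP 6.0 places the two lead-in subjects in the full-dose condition. SAP 9.9.3 adds them to the 125 mg group, but only for the effect analyses.

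**The concern.** The vital-signs paragraph is the only one in the section that names no grouping, so it can be taken to mean one table for everybody. That matters because Protocol 7.2.1 expects clear rises in blood pressure and heart rate at 125 mg, while Protocol 2.4 expects a narrower range of effects at 25 mg. A combined table would dilute the full-dose rise and the share of subjects above the cutoff.

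The other tables raise a different doubt. Only active-placebo subjects enter Stage 2, and every session there is 125 mg. Kept under their Stage 1 heading, those sessions would sit in the 25 mg column. The lead-in subjects were never randomized, so they have no Stage 1 group in the strict sense, and no rule in 9.9.4 places them. The Safety population is everyone treated, so these data are in scope. Collecting safety data is a stated purpose of the trial.

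**Working it through.** **Inputs.** SAP Table 1 gives 2 lead-in, 5 full-dose and 3 active-placebo subjects, and up to 3 in Stage 2 (call this k). There are two sessions per subject per stage, all assumed completed. Check: 2 + 5 + 3 = 10, the total in SAP 6.0.

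**If vital signs were pooled over dose.** At Visits 4 and 8 the low-dose share is 3/10 = 30%, or 3/8 = 37.5% without the lead-ins. With F the full-dose mean, L the low-dose mean and D = F − L:

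pooled mean = 0.7F + 0.3L = F − 0.30D.

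The documents give no D. Assuming 10, 20 or 30 mmHg systolic, the shortfall is 3, 6 or 9 mmHg. For cutoff counts, if no low-dose subject exceeds, 1/7 (14%) would show as 1/10 (10%), and 3/7 (43%) as 3/10 (30%).

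**If Stage 2 were totalled under the Stage 1 heading.** The 125 mg share of the 25 mg column is 2k/(6 + 2k):

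| k | 125 mg sessions | all sessions in column | share |
|---|---|---|---|
| 0 | 0 | 6 | 0% |
| 1 | 2 | 8 | 25% |
| 2 | 4 | 10 | 40% |
| 3 | 6 | 12 | 50% |

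The arithmetic is sound. What decides the point is whether the plan asks for either kind of pooling.

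**Vital signs.** The 9.9.4 wording gives the statistics and the times. It does not say that doses are combined, and nothing in it excludes group columns. A single pooled table could not deliver the comparison in SAP 4.3; a table by dose does, and it also follows Protocol 12.0.

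**Reactions, SUD and C-SSRS.** Reactions are shown for each session, and the other two by time period. In the Time and Events tables, Stage 1 sessions are Visits 4 and 8 and Stage 2 sessions are Visits 14 and 18. Rows by session or visit therefore hold one dose per Stage 1 group, and the shares above do not arise. They would need a total across stages, which the SAP does not specify for reactions or SUD. For C-SSRS the cumulative sentence names the end of each stage, which is naturally read as two cut-offs. Reactions also enter the adverse-event incidence tables, which are split by group and stage.

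**Lead-ins.** Their dose is not in doubt. The full-dose column holds 5 subjects without them (2 × 5 = 10 sessions) or 7 with them (2 × 7 = 14 sessions). Every session in it is 125 mg either way, so this is a choice of layout.

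**Data outside a table.** SAP 9.0 sends data that the plan does not analyse to the listings. That is a stated default for anything a table by Stage 1 group does not cover.

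**The case for a change.** The best case for an edit is that SAP 9.0 declares itself an amendment of the protocol's analysis plan, so Protocol 12.0 cannot be relied on to fill a silence in the SAP. The general instruction in SAP 9.9 to report by treatment group covers primary, secondary and exploratory endpoints and does not name safety measures. Visit rows do not separate the doses at Visits 4 and 8, which both arms share. The remedy would be a few words and table shells, with no new data.

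Part of this stands. The phrase is missing, and the neighbouring paragraphs show how easily it could have been included. But the amendment in SAP 9.0 is explained by how hard it is to test effectiveness with groups of 3 and 5. That is a reason to set aside t-tests and ANOVAs, and it gives no ground for dropping descriptive statistics by dose. Even without the protocol, SAP 4.3 is part of the same SAP and requires groups to be compared. The placement argument for reactions, SUD and C-SSRS is weaker still, because separate visit rows remove the mixing. The one place where a total across stages is conceivable is the cumulative C-SSRS count, and the sentence itself names both stage ends.

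**Conclusion.** No change follows. This is a missing detail that analysts would fill correctly from the rest of the plan, with vital signs tabulated by dose group and Stage 2 sessions in their own rows. The possible distortion (30% of the dose difference at each shared visit, and up to 6 of 12 sessions in the 25 mg column) depends on pooling that the SAP does not prescribe. The mmHg figures rest on assumed dose differences, and the session counts on full completion.

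All the tables concerned are descriptive. Adverse-event and serious adverse-event incidence is already shown by treatment group and stage, and no effect analysis is touched. Repeating the grouping phrase in the vital-signs paragraph would be tidy, but it would not alter any conclusion the trial can draw.

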9.10 Timing of Analyses

The primary effect analysis will be conducted after all subjects complete Stage 2, but before all long-term follow-up data have been collected. Subsequent analyses on this data set will not be conducted after initial analyses are performed, unless for further exploratory post-hoc analyses. Changes to protocol will not occur after primary analysis.

10.0 Statistical Software

Data manipulation, tabulation of descriptive statistics, calculation of inferential statistics, and graphical representations will be performed primarily using SAS (release 9.3 or higher) for Windows. If the use of other software is warranted, the final clinical study report will detail what software was used and for what purposes.

